9.9. Limitations of the research methods

Even though HIRA claims data is from the whole population of Korea, the data is not collected for research purpose. Its original purpose was to claim reimbursement. There might be intentional or unintentional miscoding of services performed and diagnosis. These errors are generally undetectable but the dominant majority of data is valid according to the previous studies on the feasibility of Korean NHI claims data.

To reduce chances of including antidepressants use for a disease other than major depressive disorders, operational definitions of at least two outpatient claims or one inpatient claims with diagnosis codes in Table 1 is used. However, it is not 100% accurate since providers are afraid of denial of reimbursement from the HIRA which is empowered with reimbursement review and denial of payment. Hence, in some cases, diagnosis code is put strategically to minimize a chance of denial. For this reason, this study focuses on antidepressants prescribed by a specialist in mental health and only analyze antidepressant prescriptions from other specialists as secondary analysis to identify antidepressant practice patterns from other specialties.

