5.2 SAFETY ENDPOINTS

Adverse outcomes are primary endpoints in this study and they include the following categories defined by KCD-7 diagnosis codes and/or NHI procedure codes appearing in medical claims data after the index date.

- GI bleeding
I850, I983, K2211, K226, K228, K250, K252, K254, K256, K260, K262, K264, K266, K270, K272, K274, K276, K280, K282, K284, K286, K290, K3181, K5521, K625, K920, K921, K922
- Fractures
S02, S12, S22, S32, S42, S52, S62, S72, S82, S92, T02, T08, T10, T12, T14.2
- Falls
W00-W19
- Intracranial hemorrhage
I60, I61, I62, I690, I691, I692, S064, S065, S066, S068
- Suicide attempt, self-harm
T40 Poisoning by narcotics and psychodysleptics [hallucinogens]
T41 Poisoning by anaesthetics and therapeutic gases
T42 Poisoning by antiepileptic, sedative-hypnotic and antiparkinsonism drugs
T43 Poisoning by psychotropic drugs, not elsewhere classified
T54 Toxic effect of corrosive substances
T60 Toxic effect of pesticides
X60-X84 intentional self-harm
- Myocardial infarction
I21.9, I21.4, I21.0, I21.1, I21.2, I21.3, I22.0A, I22.0B, I22.0C, I22.8A, I22.8B, I22.8C, I22.8D, I22.8E, I22.8F, I22.8G, I22.8H, I22.8I, I22.8, I22.9, I22.1A, I22.1B, I22.1C
- Epilepsy/seizures
G40.XX
- Stroke
 - Transient ischemic attack
G459, I63, I693
 - Hemorrhagic stroke
I60, I61, I62, I690, I691, I692
 - Ischemic stroke
I63

[NOTE] Hospitalization and CT or MRI codes such as brain CT or MRI procedure code for ischemic stroke and hemorrhagic stroke, or any CT or MRI for systemic embolism are also required for identification.

- Brain CT
HA441, HA451, HA461, HA471, HA851
- Brain MRI
HE101, HE102, HE135, HE201, HE202, HE235, HE301, HE302, HE401, HE402, HE501, HE502, HE535
- Any CT or MRI or CT

HA401-HA416, HA424, HA425, HA434, HA435, HA443-HA449, HA453, HA456-HA459, HA463-HA469, HA473-HA479, HA496, HA497, HA801, HA805, HA809, HA813, HA834, HA835, HA853, HA856, HA857-HA859, S852

- MRI
HE103-HE142, HE203-HE234, HE236-HE241, HE303-HE334, HE403-HE434, HE430-HE434, HE503-HE534, HE536-HE541, HF101, HF102, HF104-HF107, HF201, HF202, HF305, HF306
- Hyponatremia
Will be identified by prescription codes for vasopressin receptor antagonists such as tolvaptan (drug code=616501ATB)

CC
I

[figure not shown]

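### Intracranial hemorrhage includes every hemorrhagic stroke code but not the hospitalization-and-imaging rule, so one code feeds two primary safety outcomes under two standards of evidence

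*SAP*

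**What the plan says.** SAP 5.2 states that "Adverse outcomes are primary endpoints in this study" and that they are "defined by KCD-7 diagnosis codes and/or NHI procedure codes appearing in medical claims data after the index date". No minimum number of claims, care setting or diagnosis position is given.

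- Intracranial hemorrhage: "I60, I61, I62, I690, I691, I692, S064, S065, S066, S068".
- Hemorrhagic stroke, under Stroke: "I60, I61, I62, I690, I691, I692".
- The bracketed note under Stroke makes further evidence a condition of identification: "Hospitalization and CT or MRI codes such as brain CT or MRI procedure code for ischemic stroke and hemorrhagic stroke". It goes on to systemic embolism, with any CT or MRI. It does not name intracranial hemorrhage.
- Myocardial infarction is a list of diagnosis codes beginning "I21.9, I21.4, I21.0, I21.1, I21.2, I21.3, I22.0A", and GI bleeding one beginning "I850, I983, K2211, K226, K228, K250, K252, K254". Neither has a setting, procedure or repeat-claim rule.

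The intracranial hemorrhage and stroke lists and the note are the same in SAP Table 3 and in protocol Table 3, so this is not a slip in one place. Protocol 9.9 accepts that diagnoses and services may be miscoded and that such errors mostly cannot be detected. It also says that the large majority of the data are valid. It gives no figure for any adverse outcome.

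**The concern.** The plan asks for an admission and a scan before it accepts an I60-I62 or I690-I692 claim as hemorrhagic stroke. It asks for neither before it accepts the same claim as intracranial hemorrhage. Both are primary, and no reason is given for the difference.

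Two things follow. First, unconfirmed codes enter the intracranial hemorrhage count. For an uncommon outcome, even a low false-positive rate inflates the incidence, and if the rate is equal across drugs it pulls relative comparisons toward 1. Protocol 9.7 plans between-drug comparisons of adverse outcomes, time-to-event models for safety and p<0.05 as the criterion, so attenuation would affect the conclusions. Second, a confirmed hemorrhage appears under two headings, and nothing tells the reader that one outcome is contained in the other.

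For myocardial infarction and GI bleeding the issue is milder: their definitions are unspecified as to setting, not inconsistent with each other. A falsely coded GI bleed could still spread further, because SAP 5.1 treats periods with such an outcome as non-adherent.

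**Working it through.** **Step 1. Compare the code lists (SAP 5.2).**

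| Code | Intracranial hemorrhage | Hemorrhagic stroke |
|---|---|---|
| I60, I61, I62 | yes | yes |
| I690, I691, I692 | yes | yes |
| S064, S065, S066, S068 | yes | no |

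All 6 hemorrhagic stroke codes are among the 10 intracranial hemorrhage codes. The other 4 are the S06 codes.

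**Step 2. Follow a claim through both definitions as written.**

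| Claim | Hemorrhagic stroke | Intracranial hemorrhage |
|---|---|---|
| I61, outpatient, no scan | rejected by the note | counted |
| I61, admitted, brain CT or MRI | counted | counted |

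**Step 3. Illustrate the size.** The plan states no figure to reproduce. It gives no event rate, sensitivity or false-positive rate for these codes, so every input here is an assumption: true risk p0 = 0.2% on the reference drug and p1 = 0.4% on the comparator (true RR 2.0), sensitivity Se = 0.90, and a false-positive rate FP equal in both groups.

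Observed risk = Se × p + FP × (1 − p). Observed RR = observed risk 1 / observed risk 0. The share of reference-group events that are real is Se × p0 / observed risk 0.

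| FP | Observed risk 0 | Observed risk 1 | Observed RR | Share real |
|---|---|---|---|---|
| 0.02% | 0.001800 + 0.000200 = 0.002000 | 0.003600 + 0.000199 = 0.003799 | 1.90 | 90% |
| 0.1% | 0.001800 + 0.000998 = 0.002798 | 0.003600 + 0.000996 = 0.004596 | 1.64 | 64% |
| 0.5% | 0.001800 + 0.004990 = 0.006790 | 0.003600 + 0.004980 = 0.008580 | 1.26 | 27% |

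With FP = 0 the observed RR is (0.90 × 0.4%) / (0.90 × 0.2%) = 2.0. Sensitivity that is equal across drugs cancels; it is the false positives that attenuate the ratio.

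**Step 4. Vary the assumptions.** With Se = 0.95, reference risk from 0.1% to 0.3% and FP from 0.02% to 0.3%, a true RR of 2.0 is observed as 1.93 down to 1.24, and the share of real events runs from 93% down to 24%. The result depends almost wholly on the ratio of the false-positive rate to the true risk, which the documents do not give.

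**The case against.** The best defense is that the note is loosely worded. It uses such-as language and mentions systemic embolism, which is not a listed outcome, so the authors may have meant it to reach further. That is possible, but the text does not say so, and two programmers could code it differently. It is a reason to clarify the text.

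It can also be said that double appearance is only a matter of reporting. SAP 3 gives hypotheses and decision rules as not applicable, and no sum or composite of the outcomes is planned. That stands: labeling one outcome as a component of the other deals with it.

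Some stronger readings are tempting, but the documents do not support them:

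- That false positives swamp the true events. This needs a false-positive rate above the true risk, such as the assumed 0.5% against 0.2%. At 0.02% the loss is small, and protocol 9.9 says most of the data are valid.
- That protocol 9.9 adopted the one-inpatient-or-two-outpatient rule because of miscoding and then withheld it here. The stated purpose of that rule is to avoid including antidepressant use for other diseases. The remark that "in some cases, diagnosis code is put strategically to minimize a chance of denial" concerns the depression diagnosis attached to a prescription; nothing says hemorrhage, infarction or bleeding codes are entered that way. Only the general miscoding statement applies.
- That a single claim is the stated rule. The SAP sets no minimum, so a single claim suffices only by silence.
- That every adverse outcome except stroke rests on an unconfirmed diagnosis. Hyponatremia is identified by a drug prescription.
- That false codes differ by drug through visit frequency. The documents do not show this. Visit counts, provider specialty and clinic class are listed covariates, and propensity matching and weighting are planned, although these would not fully handle visits after the index date.
- That the primary myocardial infarction and GI bleeding definitions must be replaced. Requiring admission or emergency care trades sensitivity for specificity, and SAP 1 places its amendments during data analysis, so replacing them would carry a post-hoc risk.

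**Conclusion.** The inconsistency is real and can be read directly from the code lists. All six hemorrhagic stroke codes count toward intracranial hemorrhage without the confirmation that the plan demands for hemorrhagic stroke. The sponsor should correct it.

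The size of the resulting bias is unknown. Under the main set of assumptions above, with false positives equal across drugs, a true RR of 2.0 would be seen as between about 1.90 and 1.26. These figures show how the bias behaves; they do not estimate it for this study. For myocardial infarction and GI bleeding the supportable conclusion is narrower: the care setting and confirmation are unspecified, and a sensitivity analysis is the proportionate response.

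**What to change.** In SAP 5.2 and in Table 3 of both documents:

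1. State that the existing note (hospitalization plus a listed brain CT or MRI code) applies to the whole intracranial hemorrhage list.
2. Report hemorrhagic stroke as a component of intracranial hemorrhage.
3. Keep the any-claim definition of intracranial hemorrhage as a sensitivity analysis.
4. Leave the primary definitions of myocardial infarction and GI bleeding unchanged, and add a sensitivity analysis restricted to inpatient or emergency-room claims.
5. Date the change, describe it as made during analysis, and report the results under both definitions.

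The work is small: the imaging codes are already listed, and inpatient and emergency-room visits are already derived for Table 3. The cost is fewer intracranial hemorrhage events and somewhat wider confidence intervals, because cases without an admission and a scan drop out of the main definition. The retained any-claim analysis will show how much that matters.

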Adherence	Primary outcome	HIRA Database	
For each of 11 study drugs chosen as index drug, adherence will be measured by MPR during the first 90 days from the index date (acute treatment phase)
 
* MPR = (Days of medication possession from the prescriptions filled in the 90 days) / (90 days + extra days of drug supply from the last prescription fill during the 90 days)
 
** For those period with any identified adverse outcome such as GI bleeding will be considered as

			non-adherent period
Drug utilization pattern in acute phase	Secondary outcome	HIRA Database	
During the first 90 day period starting from the index date, the following types of drug utilization pattern is recorded
 
 - monotherapy (kept on the index medication) - switching (switched to other antidepressant) - combination (adding other antidepressant) - augmentation (adding other non-AD drug such as antipsychotic)
Drug utilization pattern in maintenance phase	Secondary outcome	HIRA Database	
During the second 90 day period (91 ~ 180 days) starting from the index date, the following types of drug utilization pattern is recorded
 
 - choice of antidepressant - monotherapy (kept on the same medication) - switching (switched to other antidepressant) - combination (adding other antidepressant) - augmentation (adding other non-AD drug such as antipsychotic)
Recurrence	Primary outcome	HIRA Database	
Recurrence was operationally defined as either one of the following was satisfied:
 
 1) inpatient episode with a diagnosis code in Table 1 2) emergency room visit with a diagnosis code in Table 1 3) suicide attempt identified by the following KCD-7 codes: 
T40 Poisoning by narcotics and psychodysleptics [hallucinogens] T41 Poisoning by anaesthetics and

PFIZER CONFIDENTIAL

			
therapeutic gases
 
T42 Poisoning by antiepileptic, sedative-hypnotic and antiparkinsonism drugs
 
T43 Poisoning by psychotropic drugs, not elsewhere classified
 
T54 Toxic effect of corrosive substances
 
T60 Toxic effect of pesticides
 
X60-X84 intentional self harm

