5.1 EFFICACY/EFFECTIVENESS ENDPOINT(S)

Medication compliance (persistence, discontinuation, adherence) along with recurrence are main primary efficacy endpoints and they are defined as follows:

1. MPR (medication possession ratio)
For each of 11 study drugs, the MPR will be calculated by (Days of medication possession from the prescriptions filled in the 180 days) / (180 days + extra days of drug supply from the last prescription fill during the 180 days)
2. Persistence
For each of 11 study drugs, the average length of treatment on the index drug during the first 180 day period (allowing 14 day permissible gap) will be

PFIZER CONFIDENTIAL

calculated. Switching, combination, augmentation, discontinuation will terminate the persistent period.

3. Discontinuation

For each of 11 study drugs chosen as index drug, the percentage of discontinuation in the first 90 days from the index date (acute treatment phase) will be measured (allowing 14 day permissible gap)

4. Adherence

For each of 11 study drugs chosen as index drug, adherence will be measured by MPR and persistence during the first 90 day and 180 day from the index date, respectively (acute treatment phase). MPR ≥ 0.75 and persistence ≥ 90 will be considered as adherence.

* For those period with any identified adverse outcome such as GI bleeding will be considered as a non-adherent period.

5. Recurrence

Recurrence during the acute treatment phase was operationally defined as either one of the following being satisfied:

- 1) Inpatient episode with a diagnosis code in Table 1
- 2) Inpatient episodes via the department of psychiatry or emergency medicine
- 3) Inpatient episode via nursing hospital
- 4) Emergency room visit with a diagnosis code in Table 1
- 5) Suicide attempt identified by the following KCD-7 codes:
 - T40 Poisoning by narcotics and psychodysleptics [hallucinogens]
 - T41 Poisoning by anaesthetics and therapeutic gases
 - T42 Poisoning by antiepileptic, sedative-hypnotic and antiparkinsonism drugs
 - T43 Poisoning by psychotropic drugs, not elsewhere classified
 - T54 Toxic effect of corrosive substances
 - T60 Toxic effect of pesticides
 - X60-X84 intentional self harm
- 6) Augmentation of the following non-AD drugs
 - Antipsychotic: amisulpride, aripiprazole, olanzapine, quetiapine, risperidone, perphenazine
 - Anticonvulsant: carbamazepine, valproic acid, lamotrigine
 - Mood stabilizer: lithium
 - Anxiolytic: buspirone
 - Thyroid hormone: levothyroxine, liothyronine

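### Six poisoning and toxic-effect categories (T40-T43, T54, T60) count as suicide attempt with no condition on intent, so accidental poisonings can enter a primary between-drug comparison

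*SAP*

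**What the plan says.** SAP 5.2 states that "Adverse outcomes are primary endpoints in this study". One of these is suicide attempt and self-harm, identified by any of seven entries found in claims after the index date. Four are poisoning categories (T40 to T43, for example "T41 Poisoning by anaesthetics and therapeutic gases"), two are toxic-effect categories ("T54 Toxic effect of corrosive substances" and "T60 Toxic effect of pesticides"), and the last is "X60-X84 intentional self-harm". The entries stand side by side. No sentence links a T code to an X60-X84 code, to a care setting or to any marker of intent.

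The same list is item 5 of the recurrence definition in SAP 5.1, introduced by "Suicide attempt identified by the following KCD-7 codes". A single item is enough: "Recurrence during the acute treatment phase was operationally defined as either one of the following being satisfied". The definition for the period after the acute phase carries item 5 over unchanged. SAP Table 3 repeats both lists. The Protocol has them too (section 9.3, Table 3), with the recurrence item worded "suicide attempt identified by the following KCD-7 codes".

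The planned use is comparative. Protocol section 8 and SAP 2.2 call for the risk of adverse outcomes to be compared between individual antidepressants. Protocol 9.7 plans time-to-event models with p<0.05 taken as significant. SAP 7.2.2 lists adverse events and recurrence, the latter by drug and by compliance, within a primary analysis.

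**The concern.** The name of the outcome asserts intent, and six of its seven entries do not. An accidental pesticide exposure, a household corrosive injury, or a mistaken double dose of a sedative or of the study drug itself can each produce a listed T code and so meet the rule. Each would then be tabulated as a suicide attempt.

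Two consequences follow for a comparison of named antidepressants. If such events are equally common on every drug, they inflate the rate and pull a true difference in suicidality toward no difference. If they are not equally common, a difference in accidental overdose would be published as a difference in suicidality. T42 and T43 cover sedatives and psychotropics, so they could pick up accidents with the dispensed drugs or with co-medication.

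There is a secondary effect on recurrence, because the same claim satisfies item 5. SAP 5.1 also treats a period with an identified adverse outcome as non-adherent. One accidental poisoning could therefore register both as recurrence and as non-adherence in the analysis that relates the two.

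**Working it through.** **Is a T code alone sufficient?** The plan states a joint condition where it wants one. In the same SAP 5.2, stroke needs hospitalization and an imaging code in addition to the diagnosis. In Table 3, mild cognitive impairment needs a diagnosis together with a neurocognitive test code. The suicide attempt list has no such wording, so each entry reads as sufficient.

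**Is intent handled elsewhere?** The limitations in Protocol 9.9 mention miscoding in general terms. The present problem exists even with perfect coding, because a correctly coded accident still meets the rule. No section excludes accidental poisoning or plans an analysis on X60-X84 alone.

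**How far does item 5 drive recurrence?** Item 2 of SAP 5.1 already counts any inpatient episode via psychiatry or emergency medicine, with no diagnosis condition. An accidental poisoning admitted through emergency medicine is a recurrence under item 2 whatever item 5 says. Item 5 adds only cases that no other item catches.

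**How large could the effect be?** The plan gives no event rate, accidental share or power for this outcome, so there is no figure to reproduce. What follows is illustration. Assumed inputs: intentional event rate 1 in the reference group and 2 in the comparator (true ratio 2.0), and unintentional rate *a* in both groups, unrelated to drug. The observed ratio is (2 + a)/(1 + a).

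Reading A, where *q* is the unintentional share of reference-group events: q = a/(1 + a), so a = q/(1 - q) and the observed ratio is 2(1 - q) + q = 2 - q.

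Reading B, where *q* is the unintentional share of all events in two groups of equal size: q = 2a/(3 + 2a), so a = 3q/[2(1 - q)].

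| | q = 0.10 | q = 0.40 |
|---|---|---|
| A: a | 0.111 | 0.667 |
| A: observed ratio, 2 - q | 1.9 | 1.6 |
| A: inflation of reference rate, 1/(1 - q) | 1.11 | 1.67 |
| A: inflation of comparator rate, (2 + a)/2 | 1.06 | 1.33 |
| B: a | 0.167 | 1.0 |
| B: observed ratio, (2 + a)/(1 + a) | 2.167/1.167 = 1.86 | 3/2 = 1.50 |

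**The other direction.** Put the ratio of 2.0 on the unintentional events instead and let intentional events be equal (ratio 1.0). With *q* again the reference-group share, the observed ratio is (1 - q) + 2q = 1 + q, that is 1.1 to 1.4. A difference in suicide attempts would be reported where none exists. This too is an assumption; the documents do not say whether accidental overdose differs by drug.

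**The case against.** The best defence is that the T codes are there on purpose. Claims may under-record intent codes, and a definition restricted to X60-X84 could miss true attempts. That stands as a reason to keep the T codes in the analysis. It does not justify the label, because the SAP neither gives this argument nor cites validation of the T codes as a marker of attempted suicide.

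Several stronger readings are tempting, and the documents do not support them:

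- A reader might infer that every poisoning or toxic-effect T code counts. Only six categories are listed.
- A reader might infer that the suicide attempt results will be wrong by a known amount. The accidental share is not given, and the cohort consists of new antidepressant users with depression claims, aged 18 to 70. The supportable statement is that accidental events can be counted.
- A reader might infer that X60-X84 alone is the correct definition. That exchanges an unknown number of false positives for an unknown loss of true attempts, and completeness of X60-X84 recording is not stated.
- A reader might infer that repairing item 5 would clear accidental poisonings out of recurrence. The overlap with item 2 means that it would not.

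The plan's safeguards help little. Propensity score matching and weighting balance patient characteristics but do not reclassify outcomes. The clinical advisors in Protocol 9.8 review summary results, which would not show intent unless the rows are separated.

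**Conclusion.** The point holds as a mismatch between label and definition in a primary safety outcome. As written, a claim in any of six T categories is a suicide attempt whatever its intent. The effect on recurrence is real but secondary.

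The size cannot be established from the documents. Under the assumption of 10% to 40% unintentional events unrelated to drug, a true ratio of 2.0 is seen as 1.9 to 1.6 if the share refers to the reference group, and as 1.86 to 1.50 if it refers to all events in two equal groups. If accidental events differ between drugs, the bias can run in either direction, so dilution should not be presented as the only possibility. The change is worth making because it is cheap and discards no events.

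**What to change.** In SAP 5.2 and Table 3, keep the combined list but name it 'poisoning or self-harm'. By drug, report two component rows built from the codes already listed:

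1. 'Intentional self-harm': X60-X84, with or without a T code.
2. 'Poisoning, intent not recorded as self-harm': a listed T code without X60-X84.

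State whether the two kinds of code are joined within a claim or within an episode of care. Draw conclusions about suicide attempt only where the X60-X84 row and the combined row agree, and say beforehand what agreement means. In SAP 5.1, repeat the recurrence analysis with item 5 limited to X60-X84 as a sensitivity analysis, and note that item 2 will still admit some of the same episodes. Align the Protocol list or record the departure. The SAP was already amended during data analysis, so date this change accordingly.

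Dropping T codes that come with an accidental-cause code is optional. Accidental-poisoning codes are not in the current lists, and their availability in the extracted data would have to be confirmed.

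The cost is SAP wording, a few extra table rows and one repeated recurrence analysis. The downside is fewer events in the X60-X84 row if external-cause codes are under-recorded; the combined row retains those events.
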